The p-value of the score test of the treatment main effect (equivalent to the log-rank test) will be calculated and presented. The number of 6-month chronic HCV infections per treatment group, the estimated vaccine efficacy and associated 95% confidence interval will be summarized by treatment group in [Table 8](#).

Secondary and sensitivity analyses of the primary efficacy outcome measure will be performed. First, the analysis will be repeated in the mITT cohort as follows:

- For subjects without HCV infection, the 6-month chronic infection endpoint will be coded as censored, with time to event defined as the elapsed time from the first vaccination to the end of the 26 month follow-up, or to the last observed visit before loss to follow-up or of a criterion listed under the censoring criteria for the mITT cohort.
- For subjects who develop HCV infection, the 6-month chronic infection endpoint will be coded as an observed event if the 6-month chronic infection endpoint definition is met, and as censored otherwise, with time to event defined as the elapsed time from the first vaccination to the date of the sample collection with available test result nearest to the target assessment date of six months after primary infection.

The reduction in chronic HCV incidence will be calculated from the hazard ratio of a stratified Cox model for the mITT population as described above ([Table 8](#)). Stratum-specific summaries will be presented in [Table 9](#).

Second, a sensitivity analysis will be performed in which a Cox model will be fit with binary indicators for membership in the vaccine as compared to the placebo group, and including female as compared to male, and CC IL28B status compared to CT/TT as fixed effects in the model rather than stratification factors. The interaction between time and gender will be assessed using the product of time and the binary indicator for gender as an interaction term in the model. Likewise, the interaction between time and IL28B status will be assessed using the product of time and the binary indicator for gender as an interaction term in the model. The interaction estimates will be provided in the report text and not included in a table. The reduction in chronic HCV incidence will be calculated from the hazard ratio of this model.

The model described above will be fit using PROC PHREG following the pseudocode below:

```
proc phreg data=dataset;
model time*status(0) = treatment gender|time il28bstatus|time;

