Ods output parameterestimates=ests(keep=HazardRatio HRUpperCL HRLowerCL);
run;
```

The p-value from the score test of the treatment main effect will be calculated and presented. Results of this sensitivity analysis will be provided in [Table 8](#).

Finally, a sensitivity analysis will be performed, in which subjects who develop HCV infection and do not go on to develop chronic infection will be treated as experiencing a competing risk in the Fine-Gray proportional hazards regression model.

Both the stratified and unstratified with interaction terms models will be fit.

```
proc phreg data=dataset;
class treatment / order=internal ref=first param=glm;
model time*status(0) = treatment / eventcode=1;
hazardratio treatment / diff=pairwise;
```

```

strata gender il28bstatus;
Ods output parameterestimates=ests(keep=HazardRatio HRUpperCL HRLowerCL);
run;

proc phreg data=dataset;
class treatment / order=internal ref=first param=glm;
model time*status(0) = treatment gender|time il28bstatus|time /
eventcode=1;
hazardratio treatment / diff=pairwise;
Ods output parameterestimates=ests(keep=HazardRatio HRUpperCL HRLowerCL);
run;

```

The same summaries as the mITT analyses will be calculated and presented. Results of this sensitivity analysis will be provided in [Table 8](#) and [Table 9](#).

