Analyses will be performed in both ATP and mITT populations. The number of incident HCV infections per treatment group and the vaccine efficacy and associated 95% confidence interval will be summarized by treatment group in [Table 10](#).

For both the standard and interval-censored versions of the Cox model, an additional sensitivity analysis will be performed in which the Cox model will be fit with binary indicators for membership in the vaccine as compared to the placebo group, female as compared to male, and CC IL28B status compared to CT/TT. The interaction between time and gender will be assessed using the product of time and the binary indicator for gender as an interaction term in the model. Likewise, the interaction between time and IL28B status will be assessed using the product of time and the binary indicator for gender as an interaction term in the model. The reduction in incident HCV incidence will be calculated from the hazard ratio of this model.

The model described above will be fit using PROC PHREG following the pseudocode below:

```
proc phreg data=dataset;
model time*status(0) = treatment gender|time il28bstatus|time;
Ods output parameterestimates=ests(keep=HazardRatio HRUpperCL HRLowerCL);
run;
```

```
proc icphreg data=dataset;
    class treatment;
model (StartInterval, EndInterval) = treatment gender|time
il28bstatus|time;
Ods output parameterestimates=ests(keep=HazardRatio HRUpperCL HRLowerCL);
run;
```

These additional sensitivity analyses will be performed in both ATP and mITT populations. Summaries will be provided in [Table 11](#).

The above analyses will be repeated using the secondary definition of incident HCV infection (See Section 3.3.3). The summaries will be presented in [Table 12](#) and [Table 13](#).

Exploratory Objective 2: To determine if AdCh3NSmut1 and MVA-NSmut HCV vaccines will reduce 9-month incidence of chronic HCV infection compared to placebo among HCV-uninfected IDU.

The analysis of this objective will follow exactly the analyses described in Section 8.1 with the following modification:

- For subjects in the ATP (mITT) cohort without HCV infection, the 9-month chronic infection endpoint will be coded as censored, with time to event defined as the elapsed time from the second (first) vaccination, to the end of 26 month follow up, or to the last observed visit before loss to follow-up or of a criterion listed under the censoring criteria for the ATP (mITT) cohort.

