 # of Subj = the number of subjects that reported at least one protocol deviation in the category specified.
 # of Dev = the total number of protocol deviations reported for the category specified.

Table 8: Vaccine Efficacy Against 6-Month Chronic HCV Infection by Treatment Group and Analysis Population

Analysis	Population	Number of Chronic HCV Infections				Vaccine Efficacy [1]	95 % CI for Vaccine Efficacy [2]	P-value [3]
		Vaccine		Placebo				
		Number of Subjects n	Total Subjects N	Number of Subjects n	Total Subjects N			
Primary Efficacy Analysis	ATP population	x	x	x	x	x.xx	x.xx, x.xx	0.xxx
Secondary Efficacy Analysis	mITT population	x	x	x	x	x.xx	x.xx, x.xx	0.xxx
Sensitivity Analyses	ATP population – Fine-Gray	x	x	x	x	x.xx	x.xx, x.xx	0.xxx
	mITT population – Fine-Gray	x	x	x	x	x.xx	x.xx, x.xx	0.xxx
	ATP population – Covariate-Adjusted	x	x	x	x	x.xx	x.xx, x.xx	0.xxx
	mITT population – Covariate-Adjusted	x	x	x	x	x.xx	x.xx, x.xx	0.xxx

Note: N = Number of subjects in specific treatment group.
 [1] Vaccine efficacy is obtained from stratified/covariate-adjusted Cox regression.
 [2] 95% CI = 95% confidence interval obtained from stratified/covariate-adjusted Cox regression.
 [3] P-value = p-value from score test comparing treatment groups obtained from Cox regression (log-rank for Primary and Secondary analyses).

Table 9: Stratum-Specific Vaccine Efficacy Against 6-Month Chronic HCV Infection by Treatment Group and Analysis Population

Analysis Population		Number of Chronic HCV Infections				Vaccine Efficacy [1]	95 % CI for Vaccine Efficacy [2]	P-value [3]
		Vaccine		Placebo				
		Number of Subjects n	Total Subjects N	Number of Subjects n	Total Subjects N			
ATP	All subjects	x	x	x	x	x.xx	x.xx, x.xx	0.xxx
	Males	x	x	x	x	x.xx	x.xx, x.xx	0.xxx
	Females	x	x	x	x	x.xx	x.xx, x.xx	0.xxx
	CC	x	x	x	x	x.xx	x.xx, x.xx	0.xxx
	CT/TT	x	x	x	x	x.xx	x.xx, x.xx	0.xxx
mITT	All subjects	x	x	x	x	x.xx	x.xx, x.xx	0.xxx
	Males	x	x	x	x	x.xx	x.xx, x.xx	0.xxx
	Females	x	x	x	x	x.xx	x.xx, x.xx	0.xxx
	CC	x	x	x	x	x.xx	x.xx, x.xx	0.xxx
	CT/TT	x	x	x	x	x.xx	x.xx, x.xx	0.xxx
ATP- Fine-Gray	All subjects	x	x	x	x	x.xx	x.xx, x.xx	0.xxx
	Males	x	x	x	x	x.xx	x.xx, x.xx	0.xxx
	Females	x	x	x	x	x.xx	x.xx, x.xx	0.xxx
	CC	x	x	x	x	x.xx	x.xx, x.xx	0.xxx
	CT/TT	x	x	x	x	x.xx	x.xx, x.xx	0.xxx
mITT -Fine Gray	All subjects	x	x	x	x	x.xx	x.xx, x.xx	0.xxx
	Males	x	x	x	x	x.xx	x.xx, x.xx	0.xxx
	Females	x	x	x	x	x.xx	x.xx, x.xx	0.xxx
	CC	x	x	x	x	x.xx	x.xx, x.xx	0.xxx
	CT/TT	x	x	x	x	x.xx	x.xx, x.xx	0.xxx

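### The covariate-adjusted Cox sensitivity models put each subject's own follow-up time on the right-hand side, so they have no finite solution and their vaccine efficacy and p-value are arbitrary

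*SAP*

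**What the plan says.** SAP section 8.1 defines the response for the primary endpoint as the time from dose 2 (ATP) or dose 1 (mITT) to the six-month assessment or to censoring. The primary model is a Cox model stratified by gender and IL28B status with treatment as the only covariate.

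A sensitivity analysis then moves gender and IL28B from strata to fixed effects and adds time interactions:

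- The text says "The interaction between time and gender will be assessed using the product of time and the binary indicator for gender as an interaction term", and then that "the interaction between time and IL28B status will be assessed using the product of time and the binary indicator for gender as an interaction term". The second sentence names the wrong indicator.
- The PHREG statement the text says to follow is "model time*status(0) = treatment gender|time il28bstatus|time".
- The fit is used for inference: "The reduction in chronic HCV incidence will be calculated from the hazard ratio of this model" and "The p-value from the score test of the treatment main effect will be calculated and presented". The Table 8 footnote confirms it: "Vaccine efficacy is obtained from stratified/covariate-adjusted Cox regression".

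The same right-hand side appears in the unstratified Fine-Gray code in 8.1 and in the PHREG code for incident infection in 8.3. The interval-censored version there reads "model (StartInterval, EndInterval) = treatment gender|time", followed by the IL28B term. For nine-month chronicity, 8.3 says "The analysis of this objective will follow exactly the analyses described in Section 8.1 with the following modification", so the model is fitted again for Table 14.

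**The concern.** The bar operator expands to main effects plus products. The right-hand side is therefore treatment, gender, IL28B, `time`, gender × `time` and IL28B × `time`. With no programming statement and no counting-process layout, `time` on the right is the value in the data set: each subject's own outcome time. The model then explains when a subject fails by when that subject fails.

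A genuine gender-by-time interaction uses running time, which has the same value for everyone in a risk set. The code does not do that, and the text never says that the product is evaluated at each event time.

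At stake are the ATP and mITT covariate-adjusted rows of Tables 8 and 14. They sit beside the primary result and are meant to show whether it survives adjustment. The interaction estimates promised for the report text come from the same fit.

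**Working it through.** **Design inputs (SAP section 5).** 292.5 ATP subjects; 14 versus 5.6 chronic infections per 100 person-years; 1.5 years; hazard ratio (HR) 0.4; two-sided alpha 0.05; power 85%. The plan's event figure reproduces:

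- Events needed: 4 × (1.960 + 1.036)² / (ln 0.4)² = 42.8, so 43.
- Events expected: 292.5 × 1.5 × (0.14 + 0.056)/2 = 43.0.

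**Why there is no maximum.** The score of the partial likelihood for the coefficient of `time` is

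U = Σ over events i of [ tᵢ − weighted mean of tⱼ over subjects with tⱼ ≥ tᵢ ].

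The failing subject has the smallest value in its own risk set, so every term is zero or negative. The sum is strictly negative at every value of all the coefficients unless every risk set is fully tied. There is no stationary point, with or without some ties. This step needs no simulation and no assumption about covariates.

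**Likelihood at the design rates.** 400 simulated trials of 292 subjects, times in whole days, mean 39.8 events. (This is below 43 because infected subjects leave the risk set: 146(1 − e^−0.21) + 146(1 − e^−0.084) = 39.4.) Assumed, not in the documents: 35% female, 40% CC, no covariate effects, no dropout. Other nuisance coefficients were held at 0. Entries are medians:

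| Time coefficient per year | log PL at HR 0.4 | log PL at HR 2.5 | Within-trial gap | Information on treatment |
|---|---|---|---|---|
| 0 | −219.3 | −235.0 | 15.8 | 9.98 |
| −10 | −77.5 | −82.7 | 4.8 | 7.88 |
| −100 | −13.1 | −13.6 | 0.3 | 2.27 |
| −1000 | −2.0 | −1.9 | 0.0 | 0.31 |
| −10000 | −1.6 | −1.6 | 0.0 | 0.00 |

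The likelihood rose monotonically in 100% of trials. Along that path the data stop separating a protective vaccine (HR 0.4) from a harmful one (HR 2.5). The score test fails too, because it needs the maximum over the time terms, which does not exist. On the same data, `treatment gender il28bstatus` gives median vaccine efficacy (VE) 0.60 (10th to 90th percentile 0.39 to 0.75); true time-dependent interactions give the same.

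**What an iterating program would return.** A second simulation used monthly visits ± 7 days, 30% female and 40% CC (again assumed), and Newton steps with step-halving; 200 trials per HR:

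- True HR 0.4, code as written: after 8 steps, VE 5th/50th/95th percentiles −1.35 / 0.24 / 0.92. After 25 steps, about −543,000 / 0.14 / 1.00, with 38.5% of estimates negative, no fit meeting a 1e-8 criterion, and Wald rejection 0%.
- True HR 0.4, time-dependent terms: 0.36 / 0.62 / 0.79; rejection 79%.
- True HR 1: rejection 0% as written, 5.5% with time-dependent terms.

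In one trial VE went from −0.05 at step 1 to 0.37 at step 8, 0.92 at step 10 and then 1.00, with a standard error rising from 0.33 to over 10,000. Without time terms the same data gave 0.61.

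**Fine-Gray code.** Subjects with a competing event stay in the risk set, so the argument above does not carry over; the maximum was finite in all 300 trials of each scenario. The model still conditions on the outcome time. Placebo clearance was ranged from 20% (protocol 2.1) to 48% (1 − 14/27, protocol 11.2 and 11.4.5); the vaccine-arm clearance hazard is assumed.

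- Vaccine moves infections to clearance: median VE 0.83 (20% cleared) or 0.71 (48%), against 0.63 in both without time terms.
- Equal clearance hazards: median stays near 0.60, but the 10th to 90th percentile range widens from 0.36–0.76 to 0.01–0.83 (20%) and from 0.37–0.78 to 0.29–0.79 (48%).

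**The case against.** The best defence is that these blocks are labelled pseudocode, with placeholder data sets and loose variable names, and that the text lists no main effect of time; that term comes only from the bar operator. Fitting the text literally (treatment, gender, IL28B and the two own-time products, no main effect) converged in 150 of 150 trials. In a Cox section, a time-by-gender interaction can also be read as a time-varying effect. Non-convergence would be obvious on the first run, and the SAP preface requires deviations to be explained in the study report.

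Part of this stands. A time-dependent interaction may well have been intended, and only sensitivity and exploratory results are touched. The likelihood grid is not a profile likelihood, though the analytic argument does not depend on it. The Fine-Gray distortion depends on the assumed clearance pattern, and Tables 8 and 9 do not say whether the stratified or unstratified Fine-Gray fit fills their rows. Table 11, to which 8.3 sends the adjusted incident-infection results, has no covariate-adjusted row.

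It does not remove the point. The SAP instructs that the model be fitted following this code, and the same construction appears in four MODEL statements. Neither text nor code defines a time-dependent term. The convergent text-only version is still biased (median VE 0.50, against 0.61 without time terms). Leaving the repair until the fit fails means choosing the model after the data are in hand.

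**Conclusion.** The concern holds. As coded, the unstratified PHREG Cox models for six-month chronicity, nine-month chronicity and incident infection have no finite maximum, and their vaccine efficacy and p-value depend on where iteration stops. The covariate-adjusted rows of Tables 8 and 14 therefore cannot speak to robustness. The Fine-Gray version is a lesser fault: finite, but biased or less precise depending on the clearance pattern. In the ICPHREG version `time` is not part of the interval response; that is mis-specified, but its numerical behaviour was not tested.

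The no-maximum result assumes only that the code is run as written, with `time` read from the data set. No SAS run was made, so what PHREG would print is inferred. The simulated sizes also rest on the SAP's rates and the assumed gender and IL28B mix. The primary stratified ATP analysis and the stratified mITT analysis are unaffected. This should be fixed before unblinding, but it does not threaten the primary result.

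**What to change.** - In the PHREG Cox code of 8.1 and 8.3, fit `treatment gender il28bstatus` and take the covariate-adjusted vaccine efficacy and score test from that model.
- If the gender-by-time and IL28B-by-time interactions are kept, in this or a separate Cox fit, define them with programming statements evaluated at each event time, with no main effect of time. State which fit supplies the reported vaccine efficacy.
- Correct the IL28B sentence in 8.1 and 8.3 to use the IL28B indicator.
- Remove `|time` from the Fine-Gray and ICPHREG code, amend the 8.1 sentence that announces the unstratified Fine-Gray fit with interactions, and say which Fine-Gray fit fills Tables 8 and 9.
- Give the adjusted incident-infection results a row in Table 11 or drop the reference to it.

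The cost is SAP text, code and table shells only. Data collection and the primary analysis do not change.

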8.2. Secondary Efficacy Analyses

There are no secondary efficacy objectives in this study.

8.3. Exploratory Efficacy Analyses

Exploratory Objective 1: To determine if AdCh3NSmut1 and MVA-NSmut HCV vaccines will reduce incidence of incident HCV infection compared to placebo among HCV-uninfected IDU.

Kaplan-Meier curves for incident HCV infection will be generated for both the ATP and mITT populations ([Figure 5](#) and [Figure 6](#)).

The reduction in incident HCV incidence will be calculated from the hazard ratio of a stratified Cox model. The stratification factors that will be used are gender and IL28B status (i.e. there will be four strata: Female & CC, Female & CT/TT, Male & CC, Male & CT/TT). The model to be fit for subject i is:

$$\log h_i(t) = \alpha_j(t) + \beta x_i$$

where $h(t)$ is the hazard function at time t , $\alpha_j(t)$ is the logarithm of the baseline hazard function for strata j , x_i is a binary indicator for membership in the vaccine as compared to the placebo group. See Section 3.3.3 for definition of incident HCV infection.

The model described above will be fit using PROC PHREG following the pseudocode below:

```

proc phreg data=dataset;
class treatment;
model time*status(0) = treatment;
strata gender il28status;
Ods output parameterestimates=ests(keep=HazardRatio HRUpperCL HRLowerCL);
run;

```

Vaccine Efficacy = 1 – Hazardratio;

Lower 95% CI= 1 – HRUpperCL which is the same as 1 – exp(estimate + $\Phi^{-1}(.975)$ *stderratio)

Upper 95% CI= 1 – HRLowerCL which is the same as 1 - exp(estimate – $\Phi^{-1}(.975)$ *stderratio)

The p-value of the score test of the treatment main effect (equivalent to the log-rank test) will be calculated and presented. Analyses will be performed in both ATP and mITT populations. The number of incident HCV infections defined as detection of viremia (RNA Reactive) per treatment group and the vaccine efficacy and associated 95% confidence interval will be summarized by treatment group in [Table 10](#). Stratum-specific summaries will be presented in [Table 11](#).

A sensitivity analysis will also be performed by repeating the above using an interval censored Cox model [12]. The model will be fit using PROC ICPHREG following the pseudocode below:

```
proc icphreg data=dataset;
    class treatment;
model (StartInterval, EndInterval) = treatment;
strata gender il28status;
Ods output parameterestimates=ests(keep=HazardRatio HRUpperCL HRLowerCL);
run;
```

Analyses will be performed in both ATP and mITT populations. The number of incident HCV infections per treatment group and the vaccine efficacy and associated 95% confidence interval will be summarized by treatment group in [Table 10](#).

For both the standard and interval-censored versions of the Cox model, an additional sensitivity analysis will be performed in which the Cox model will be fit with binary indicators for membership in the vaccine as compared to the placebo group, female as compared to male, and CC IL28B status compared to CT/TT. The interaction between time and gender will be assessed using the product of time and the binary indicator for gender as an interaction term in the model. Likewise, the interaction between time and IL28B status will be assessed using the product of time and the binary indicator for gender as an interaction term in the model. The reduction in incident HCV incidence will be calculated from the hazard ratio of this model.

The model described above will be fit using PROC PHREG following the pseudocode below:

```
proc phreg data=dataset;
model time*status(0) = treatment gender|time il28bstatus|time;
Ods output parameterestimates=ests(keep=HazardRatio HRUpperCL HRLowerCL);
run;
```

```
proc icphreg data=dataset;
    class treatment;
model (StartInterval, EndInterval) = treatment gender|time
il28bstatus|time;
Ods output parameterestimates=ests(keep=HazardRatio HRUpperCL HRLowerCL);
run;
```

These additional sensitivity analyses will be performed in both ATP and mITT populations. Summaries will be provided in [Table 11](#).

The above analyses will be repeated using the secondary definition of incident HCV infection (See Section 3.3.3). The summaries will be presented in [Table 12](#) and [Table 13](#).

Exploratory Objective 2: To determine if AdCh3NSmut1 and MVA-NSmut HCV vaccines will reduce 9-month incidence of chronic HCV infection compared to placebo among HCV-uninfected IDU.

The analysis of this objective will follow exactly the analyses described in Section 8.1 with the following modification:

- For subjects in the ATP (mITT) cohort without HCV infection, the 9-month chronic infection endpoint will be coded as censored, with time to event defined as the elapsed time from the second (first) vaccination, to the end of 26 month follow up, or to the last observed visit before loss to follow-up or of a criterion listed under the censoring criteria for the ATP (mITT) cohort.
- For subjects in the ATP (mITT) cohort who develop HCV infection, the 9-month chronic infection endpoint will be coded as an observed event if the 9-month chronic infection endpoint definition is met, and as censored otherwise, with time to event defined as the elapsed time from the second (first) vaccination to the date of the sample collection with available test result nearest to the target assessment date of nine months after primary incident infection.

Kaplan-Meier curves will be presented in [Figure 7](#) and [Figure 8](#). Regression model summaries will be presented in [Table 14](#) and [Table 15](#).

Exploratory Objective 3: To determine if AdCh3NSmut1 and MVA-NSmut HCV vaccines will reduce peak concentration (magnitude) of HCV RNA compared to placebo, in blood samples of persons with incident HCV infection.

HCV RNA concentrations will be summarized by treatment group and by each month from HCV Infection for the ATP and mITT populations. Summaries will include n (number observed), minimum, maximum, geometric mean and the associated 95% confidence interval as well as geometric fold rise from the concentration at the first HCV RNA detection and the associated 95% confidence interval ([Table 16](#), [Table 17](#), [Table 18](#), [Table 19](#)). For each subject, the peak concentration from the first HCV RNA detection to the 6 month blood collection will be identified. The logarithmic peak concentrations will be compared between the vaccine and placebo groups using a two-sided t-test ([Table 20](#) and [Table 21](#)).

Exploratory Objective 4: To determine if AdCh3NSmut1 and MVA-NSmut HCV vaccines will reduce duration of HCV viremia (shorter time to spontaneous resolution) during incident infection (6-month period following incident HCV infection) compared to placebo in blood samples of persons with incident HCV infection.

The duration of incident infection (time to spontaneous resolution) is expected to decrease 4-fold in vaccinated subjects who develop viremia (similar to that observed in subjects with HCV reinfection), compared to the placebo group, after 6 months of observation following incident infection. The midpoint between infection and clearance dates will be used to determine duration as previously described (Section 3.3.5). For subjects without observed clearance, the resolution endpoint will be coded as censored, with time to event defined as the elapsed time from the incident infection, to the end of the 6 month follow up, or to the last observed visit before loss to follow-up or to the earliest time any criterion listed under the censoring criteria for the ATP (or mITT) cohort was met.

Analyses of this objective will follow the proportional hazards analysis plan for the primary outcome. Kaplan-Meier curves will be presented in [Figure 9](#) and [Figure 10](#). Regression model summaries will be presented in [Table 22](#) and [Table 23](#). Summary statistics of duration will be presented in [Table 24](#).

Exploratory Objective 5: To determine if AdCh3NSmut1 and MVA-NSmut HCV vaccines will reduce incidence of chronic HCV infection with genotype 1 compared to non-genotype 1 among HCV-uninfected IDU.

A chronic HCV infection genotype 1 will be defined as a chronic HCV infection at 6 months, as defined in Section 3.3.2, with the additional requirement that the infection is genotype 1 as determined from blood samples obtained at the first HCV viremic visit, provided sufficient sample is available.

Because the vaccine is developed from HCV genotype 1b sequences, we hypothesize that we may see greater reduction in chronic infection with HCV genotype 1, compared to other genotypes as a result of stronger genotype specific immune responses: 75% reduction in chronic infection with genotype 1 compared to 45% reduction in chronic infection with non-1 genotypes. These exploratory analyses will be based on estimates of the incidence of HCV genotype 1 infection and non-1 genotypes in each study group using methods for censored survival regression with competing risks (Fine-Gray proportional hazards).

Analyses of this objective will follow the Fine-Gray proportional hazards analysis plan for the Primary Efficacy Objective where two separate models will be fit:

- The primary event of interest is chronic HCV with genotype 1 and the competing event is chronic HCV with genotype other than 1.
- The primary event of interest is chronic HCV with genotype other than 1 and the competing event is chronic HCV with genotype 1.

Kaplan-Meier curves will be presented in [Figure 11](#) and [Figure 12](#). Regression model summaries will be presented in [Table 25](#) and [Table 26](#).

Additional Exploratory Analyses

A summary of study rates by treatment group and site are provided in [Table 27](#) and [Table 28](#), respectively.

With regard to the primary efficacy endpoint, as all possible cases, including cases with uncertain classification for chronicity, will be reviewed by a blinded independent endpoint review committee (ERC) to make a determination of infection outcome. This committee will be comprised of the study PIs, HCV experts, and the SDCC. An interim case review committee comprised of HCV experts, the SDCC, and DMID met on October 14, 2016 and the members were concerned that the endpoint definition in the protocol does not account for subjects with mixed genotype infections; so, if a person's dominant genotype changes over the 6-month period, per the protocol, the subject would not be included as a 6-month chronically infected endpoint case but, in practice, the person still has chronic HCV infection. It was proposed that in addition to the "per protocol" assessments, that the ERC voting members provide their "real-world" and "expert clinical" assessment. The Committee asked that an exploratory analysis of 6-month and 9-month chronicity be conducted using their "expert clinical" non-per protocol assessment of chronic infections to include these more complex cases of potential mixed infections and to include subjects who miss the 6-month visit window, but remain viremic afterwards.

At the final ERC review, the committee will determine case status per protocol as well as ERC-defined cases. The number of 6 and 9 month chronic HCV infections as determined by the ERC per treatment group and the vaccine efficacy and associated 95% confidence interval will be summarized by treatment group in [Table 29](#) and [Table 30](#) for the mITT and ATP populations.

Subject listings of HCV infection status and HCV positive quantitative results are provided in [Listing 24](#) and [Listing 25](#), respectively. A listing of genotyping results, sequence evaluation and ERC Assessment is provided in [Listing 26](#).

